9.3.2. Unsolicited Adverse Events

When calculating the incidence of unsolicited AEs (i.e., on a per subject basis), each subject will only be counted once at the highest severity and/or relationship, and any repetitions of AEs within a subject will be ignored; the denominator will be the total number of subjects in the safety population. All AEs reported will be included in the summaries and analyses.

The number and percentage of subjects reporting at least one unsolicited AE will be summarized by MedDRA system organ class and preferred term. A 95% CI will be presented for the percentage of subjects reporting any unsolicited AE (serious or non-serious) for each MedDRA system organ class and preferred term over all study vaccinations (Table 94 and Table 95).

The following summaries for unsolicited AEs will be presented by MedDRA system organ class, preferred term, and treatment arm:

- Incidence of AEs by severity and relationship to study product (Table 96);
- Incidence of non-serious, related AEs by severity (Table 97);
- Incidence of AEs over time (Days 1-8, Days 9-22 post each study vaccination) (Table 98);
- Incidence of non-serious, related AEs over time (Days 1-8, Days 9-22 post each study vaccination) (Table 99) note this table presents results for secondary safety endpoint, "Occurrence of study vaccine-related unsolicited non-serious AEs from the time of each study vaccination through approximately 21 days after each study vaccination";
- Total frequency of AEs over time (Days 1-8, Days 9-22 post each study vaccination) (Table 100);
- Subject listing of non-serious AEs of moderate or greater severity (Table 104);
- Bar chart displaying total frequency of AEs by severity and MedDRA system organ class, Treatment Arm, and Age Stratum (Figure 21);

- Bar chart displaying incidence of AEs by severity and MedDRA system organ class, Treatment Arm, and Age Stratum (Figure 22);
- Bar chart displaying total frequency and incidence of AEs by relationship to study product and MedDRA system organ class, Treatment Arm and Age Stratum (Figure 23 and Figure 24).

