11.4.2 Subject Enrollment and Follow-up

Based on the accrual rates observed in similar studies, it seems reasonable to expect that the participating VTEUs will be able to enroll this trial in a timely fashion. In previous DMID trials of A/H7N9 vaccines, 5 VTEUs recruited 975 healthy adults ages 19-64 in 10 weeks, and 10 VTEU sites (or sub-contracted sites) recruited 479 healthy adults \geq 65 years old in 14 weeks. Prior experience suggests up to 5% of subjects ages 19 – 64, and 12% of subjects ages \geq 65 may be excluded from the per protocol analysis for the primary immunogenicity outcome either because they did not receive the second study vaccination, were lost-to-follow-up, or because they had a protocol deviation requiring their exclusion from the per protocol analysis.

Within the 19-64 years age stratum, over enrollment up to 5% is allowed, to ensure a minimum of n=100 per adjuvanted treatment arm and n=50 per unadjuvanted treatment arm are available for the primary immunogenicity analysis. Within the ≥ 65 years treatment arm a minimum of 60 subjects are planned to enroll in each adjuvanted treatment arm and a minimum of 30 subjects are planned to enroll in each unadjuvanted treatment arm to ensure at least 50 subjects in each adjuvanted arm and 25 subjects in each unadjuvanted arm are available for analysis of the primary immunogenicity endpoint. Enrollment within this age stratum may continue up to approximately 75 subjects per adjuvanted arm and approximately 38 subjects per unadjuvanted arm.

Follow-up will consist of 2 segments. The first encompasses the core data for this trial and will consist of results for all study visits through approximately 21 days after the last study vaccination. The second segment consists of a 6-month immunogenicity assessment and follow-up safety assessments through approximately 12 months after the last study vaccination.

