6.3. Analysis Populations

6.3.1. Safety Population

The Safety Analysis population includes all subjects who received at least one study vaccination.

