9.3.1. Solicited Events and Symptoms

Systemic solicited adverse events were collected pre-vaccination, and systemic and local solicited adverse events were collected at-least 20 minutes post-vaccination and then daily for 7 days after each vaccination and graded on a scale of 0 (absent), 1 (mild), 2 (moderate) and 3 (severe). Systemic events include fever, feverishness, fatigue, malaise, myalgia, arthralgia, headache, and nausea. The grading scale for systemic events, including quantitative grading for fever, is included in Table 11. Local events include pruritus, ecchymosis, erythema, induration/swelling, pain, and tenderness. Ecchymosis, erythema, and induration are measured by both functional and measurement grading scales as defined in Table 10.

When calculating the incidence of solicited events, each subject will be counted once at the highest severity following the applicable vaccination, and any repetitions will be ignored. For summaries presented separately for each vaccination, the denominator for percentages will be the number of subjects who received the respective vaccination with non-missing data for the event summarized. For summaries over all vaccinations the denominator will be the number of subjects who received at least one vaccination with non-missing data for the event summarized.

The number and percentage of subjects reporting at least one solicited adverse event of any severity will be summarized for each solicited symptom, any systemic symptom, any local symptom, and any symptoms. For each event the denominator is the number of subjects who received the applicable vaccination with non-missing data for the specific event. The 95% CI calculated using Clopper-Pearson methodology from a binomial distribution (SAS Proc Freq with a binomial option) will be presented (Table 75, Table 76, Table 77, Table 78, Table 79, and Table 80). Logistic regression models will be fit to estimate the effect of treatment and age on the probability of reporting any local event or reporting any systemic event (Table 81 and Table 82). If statistically significant effects are observed in the model for local events or systemic events, then additional models will be fit for each individual event of that type.

$$logit[P(Event)] = \beta_0 + \beta_1 \times Treatment + \beta_2 (Age \ge 65) + \varepsilon,$$

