10. REPORTING CONVENTIONS

P-values ≥0.001 and ≤0.999 will be reported to 3 decimal places; p-values less than 0.001 will be reported as "<0.001"; p-values greater than 0.999 will be reported as "> 0.999". The mean, standard deviation, and any other statistics other than quantiles, will be reported to one decimal place greater than the original data. Quantiles, such as median, or minimum and maximum will use the same number of decimal places as the original data. Proportions will be presented as two decimal places; values <0.01 will be presented as "<0.01". Percentages will be reported to the nearest whole number; non-zero values < 1% will be presented as "<1"; values greater than 99% but less than 100% will be presented as >99. Estimated parameters, not on the same scale as raw observations (e.g. regression coefficients) will be reported to 3 significant figures.

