Table 77: Number and Percentage of Subjects Experiencing Solicited Events with 95% Confidence Intervals by Symptom and Treatment Arm Post Study Vaccination 2 – Safety Population *

[Footnote update] N = Number of subjects in the Safety Population who received the second vaccination.

Table 78: Number and Percentage of Subjects Experiencing Solicited Events with 95% Confidence Intervals by Symptom, Treatment Arm and Age Stratum Post Any Study Vaccination – Safety Population *

	3.75	Group 1 5 mcg A/F + AS03 (N=X)		7.5	Group 2 mcg A/H + AS03 (N=X)		15	Group 3 mcg A/H' + AS03 (N=X)		15	Group 4 mcg A/H (N=X)		45	Group 5 mcg A/H (N=X)	
Symptom	n	%	95% CI	n	%	95% CI	n	%	95% CI	n	%	95% CI	n	%	95% CI
	l					Age 19) -64	l			l				.I
Any Symptom	х	XX	xx-xx	X	xx	xx-xx	X	xx	xx-xx	X	xx	xx-xx	X	xx	xx-xx
Any Systemic Symptom	х	XX	xx-xx	X	xx	xx-xx	X	XX	xx-xx	X	XX	xx-xx	X	XX	xx-xx
Fever	X	XX	xx-xx	X	XX	xx-xx	X	XX	xx-xx	X	XX	xx-xx	X	XX	xx-xx
Feverishness	X	XX	xx-xx	X	XX	xx-xx	X	XX	xx-xx	X	XX	xx-xx	X	XX	xx-xx
Fatigue	X	XX	xx-xx	X	XX	xx-xx	X	XX	xx-xx	X	XX	xx-xx	X	XX	xx-xx
Malaise	X	XX	xx-xx	X	XX	xx-xx	X	XX	xx-xx	X	XX	xx-xx	X	XX	xx-xx
Myalgia	X	XX	xx-xx	X	XX	xx-xx	X	XX	xx-xx	X	XX	xx-xx	X	XX	xx-xx
Arthralgia	X	XX	xx-xx	X	XX	xx-xx	X	XX	xx-xx	X	XX	xx-xx	X	XX	xx-xx
Headache	X	XX	xx-xx	X	XX	xx-xx	X	XX	xx-xx	X	XX	xx-xx	X	XX	xx-xx
Nausea	X	XX	xx-xx	X	XX	xx-xx	X	XX	xx-xx	X	XX	xx-xx	X	XX	xx-xx
Any Local Symptom	X	XX	xx-xx	X	XX	xx-xx	X	XX	xx-xx	X	XX	xx-xx	X	XX	xx-xx
Pain	X	XX	xx-xx	X	XX	xx-xx	X	XX	xx-xx	X	XX	xx-xx	X	XX	xx-xx
Tenderness	X	XX	xx-xx	X	XX	xx-xx	X	XX	xx-xx	X	XX	xx-xx	X	XX	xx-xx
Pruritus	X	XX	xx-xx	X	XX	xx-xx	X	XX	xx-xx	X	XX	xx-xx	X	XX	xx-xx
Ecchymosis	X	XX	xx-xx	X	XX	xx-xx	X	XX	xx-xx	X	XX	xx-xx	X	XX	xx-xx
Ecchymosis (measurement)	X	XX	xx-xx	X	XX	xx-xx	X	XX	xx-xx	X	XX	xx-xx	X	XX	xx-xx
Erythema	X	XX	xx-xx	X	XX	xx-xx	X	XX	xx-xx	X	XX	xx-xx	X	XX	xx-xx
Erythema (measurement)	X	XX	xx-xx	X	XX	xx-xx	X	XX	xx-xx	X	XX	xx-xx	X	XX	xx-xx
Induration/Swelling	X	XX	xx-xx	X	XX	xx-xx	X	XX	xx-xx	X	XX	xx-xx	X	XX	xx-xx

Table 78: Number and Percentage of Subjects Experiencing Solicited Events with 95% Confidence Intervals by Symptom, Treatment Arm and Age Stratum – Post Any Study Vaccination – Safety Population (continued)

	3.75	Group 1 5 mcg A/F + AS03 (N=X)		7.5	Group 2 mcg A/H + AS03 (N=X)		15	Group 3 mcg A/H' + AS03 (N=X)		15	Group 4 mcg A/H (N=X)		45	Group 5 mcg A/H (N=X)	
Symptom	n	%	95% CI	n	%	95% CI	n	%	95% CI	n	%	95% CI	n	%	95% CI

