	Ages 19-64	Subjects with No Symptoms	x (%)	x (%)	x (%)

Table 92: Number and Percentage of Subjects Experiencing Solicited Systemic Events for Dose 1 Compared with Dose 2 by Treatment Arm and Age Stratum – Safety Population (continued)

				Study Vaccination 2	
Treatment Arm	Age Stratum	Study Vaccination 1	Subjects with No Symptoms	Subjects with Mild or Greater Symptoms	Total Number of Subjects n (Percent) [p-value*]
Group 4 15 mcg		Subjects with Mild or Greater Symptoms	x (%)	x (%)	x (%)
A/H7N9		Total Number of Subjects	x (%)	x (%)	x (100%) [0.xxx]
	Ages ≥ 65	Subjects with No Symptoms	x (%)	x (%)	x (%)
		Subjects with Mild or Greater Symptoms	x (%)	x (%)	x (%)
		Total Number of Subjects	x (%)	x (%)	x (100%) [0.xxx]
	All Subjects	Subjects with No Symptoms	x (%)	x (%)	x (%)
		Subjects with Mild or Greater Symptoms	x (%)	x (%)	x (%)
		Total Number of Subjects	x (%)	x (%)	x (100%) [0.xxx]
Group 5 45 mcg	Ages 19-64	Subjects with No Symptoms	x (%)	x (%)	x (%)
A/H7N9		Subjects with Mild or Greater Symptoms	x (%)	x (%)	x (%)
		Total Number of Subjects	x (%)	x (%)	x (100%) [0.xxx]
	Ages ≥ 65	Subjects with No Symptoms	x (%)	x (%)	x (%)
		Subjects with Mild or Greater Symptoms	x (%)	x (%)	x (%)
		Total Number of Subjects	x (%)	x (%)	x (100%) [0.xxx]

Table 92: Number and Percentage of Subjects Experiencing Solicited Systemic Events for Dose 1 Compared with Dose 2 by Treatment Arm and Age Stratum – Safety Population (continued)

			Study Vaccination 2							
Treatment Arm	Age Stratum	Study Vaccination 1	Subjects with No Symptoms	Subjects with Mild or Greater Symptoms	Total Number of Subjects n (Percent) [p-value*]					
	All Subjects	Subjects with No Symptoms	x (%)	x (%)	x (%)					
		Subjects with Mild or Greater Symptoms	x (%)	x (%)	x (%)					
		Total Number of Subjects	x (%)	x (%)	x (100%) [0.xxx]					

Note: Denominators for percentages are the number of subjects in the safety population who received both the first and second study vaccination. [x] subjects did not get the second dose and are not included in this table.

Table with similar format:

Table 93: Number and Percentage of Subjects Experiencing Solicited Local Events for Dose 1 Compared with Dose 2 by Treatment Arm and Age Stratum – Safety Population

^{*} P-value is calculated from McNemar's test for each group and age stratum pair.

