[Repeat for Ages 19-64 and \geq 65]	1			•			•	•		•		•		•	
		ı	Repeat	for all t	reatmen	t arms]									

Note: N = Number of subjects in the Safety Analysis Population. This table presents number and percentage of subjects. For each time period, a subject is only counted once per PT.

Table 99: Number and Percentage of Subjects Experiencing Non-Serious, Related Unsolicited Adverse Events Within 21 Days Post Vaccination by MedDRA System Organ Class and Preferred Term, Study Vaccination, Treatment Arm and Age Stratum – Safety Population

			y 1-8 Vac 1	Day Post			Day 1-22 Post Vac 1 Post Vac 2 Post Vac 2		Day 1-22 Post Vac 2		Day 1-22 Post Any Vaccinatio				
MedDRA System Organ Class	MedDRA Preferred Term	n	%	n	%	n	%	n	%	n	%	n	%	n	%
		Group	p 1 3.75	mcg A/l	H7N9 +	AS03 (N=X)								
All Subjects															
Any SOC	Any PT	х	xx	X	XX	X	xx	х	xx	х	xx	х	XX	x	xx
[SOC 1]	Any PT														
	[PT 1]														
	[PT 2]														
[SOC 2]	Any PT														
	[PT 1]														
	[PT 2]														
[Repeat for Ages 19-64 and \geq 65]	•	•	•				•		•				•	•	
		ſ	Repeat	for all ti	eatmen	t arms]									

Table 100: Number of Unsolicited Adverse Events by MedDRA System Organ Class and Preferred Term, Day Post Vaccination, Treatment Arm and Age Stratum – Safety Population

		Day 1-8 Post Vac 1	Day 9-22 Post Vac 1	Day 1-22 Post Vac 1	Day 1-8 Post Vac 2	Day 9-22 Post Vac 2	Day 1-22 Post Vac 2	Day 1-22 Post Any Vaccination
MedDRA System Organ Class	MedDRA Preferred Term	# of Events	# of Events	# of Events	# of Events	# of Events	# of Events	# of Events
	(Group 1 3.75 n	ncg A/H7N9 +	AS03 (N=X)				
All Subjects								
Any SOC	Any PT	x	X	X	X	X	X	X
[SOC 1]	Any PT							
	[PT 1]							
	[PT 2]							
[SOC 2]	Any PT							
	[PT 1]							
	[PT 2]							
[Repeat for Ages 19-64 and \geq 65]								
		[Repeat fo	r all treatmer	nt arms]				
Note: $N = Number of subjects in th$	e Safety Analysis Population. T	his table presen	ts number of e	vents; a subject	may be counted	multiple times.		

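### Post-vaccination-2 percentages of unsolicited AEs (SAP Tables 98 and 99) are taken over everyone who received dose 1, so they fall below the incidence among dose-2 recipients

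*SAP*

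**What the plan says.** SAP 9.3.2 gives one rule for the incidence of unsolicited AEs: "the denominator will be the total number of subjects in the safety population". SAP 6.3.1 defines that population: "The Safety Analysis population includes all subjects who received at least one study vaccination". The denominator is therefore everyone who received dose 1.

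The same section plans Table 98 (all unsolicited AEs) and Table 99 (related, non-serious unsolicited AEs) by time window after each vaccination. Both shells have Post Vac 2 columns for Days 1-8, 9-22 and 1-22. The Table 98 footnote repeats the rule, "N = Number of subjects in the Safety Analysis Population. This table presents number and percentage of subjects. For each time period", and gives no separate N for vaccination 2. The Table 99 shell shows no denominator note, but its title refers to the Safety population and nothing in it departs from 9.3.2. SAP 9.3.2 also identifies Table 99 as the result for the secondary safety endpoint on related non-serious unsolicited AEs after each vaccination.

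Solicited events are handled differently. For summaries by vaccination, SAP 9.3.1 says "the denominator for percentages will be the number of subjects who received the respective vaccination with non-missing data for the event summarized", and the Table 77 footnote for vaccination 2 reads "N = Number of subjects in the Safety Population who received the second vaccination".

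**The concern.** A subject who did not receive dose 2 has no period after dose 2. Under the 9.3.2 rule that subject is still counted in the denominator of every Post Vac 2 column. In addition, at the contacts that follow dose 2, Protocol 8.2.4 to 8.2.6 limit AE collection in such subjects to serious events, medically attended events and the related special categories. The ordinary non-serious events that Table 99 reports are not collected from them there.

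So the Post Vac 1 columns show incidence among people exposed to the dose, and the Post Vac 2 columns do not. A reader comparing the two doses across a row of Table 99 is comparing two different quantities, with no note saying so. The difference always makes dose 2 look slightly better tolerated. It could also vary by arm if dose 2 is missed unequally, but the documents give no arm-specific rates.

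Only the Post Vac 2 columns of Tables 98 and 99 are affected. Tables 94 to 97, the event counts in Table 100, and the Post Vac 1 and any-vaccination columns are not.

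**Working it through.** The plan has no figure to reproduce here, because Tables 98 and 99 are empty shells. The size follows from the definitions.

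**Formula.** Let r be the incidence among dose-2 recipients and w the share of the Safety population without dose 2. Then reported % = r × (1 − w), and the gap is r × w.

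**Inputs.**
- Arm sizes (SAP section 5): 100 aged 19-64 and 60 aged 65 and over per adjuvanted arm; 50 and 30 per unadjuvanted arm.
- w is not given. Protocol 11.4.2 expects up to 5% (19-64) and 12% (65 and over) to be excluded from the per-protocol analysis, "either because they did not receive the second study vaccination, were lost-to-follow-up, or because they had a protocol deviation requiring their exclusion". These figures cover several causes, so the share without dose 2 alone is probably smaller. I use them as planning ceilings.
- All-age ceiling: (0.05 × 100 + 0.12 × 60)/160 = 12.2/160 = 7.6%. For unadjuvanted arms, (0.05 × 50 + 0.12 × 30)/80 = 6.1/80 = 7.6%.

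**Effect on an illustrative r of 20%.**

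| Group | w at ceiling | Reported % at ceiling | Reported % at half the ceiling |
|---|---|---|---|
| 19-64 | 5% | 20 × 0.95 = 19.0 | 20 × 0.975 = 19.5 |
| All ages | 7.6% | 20 × 0.924 = 18.5 | 20 × 0.962 = 19.2 |
| 65 and over | 12% | 20 × 0.88 = 17.6 | 20 × 0.94 = 18.8 |

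**Incidence at which the gap reaches one percentage point.** Setting r × w = 0.01 gives r = 0.01/w: 20.0% for w = 5%, 13.1% for w = 7.6% and 8.3% for w = 12%.

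**What would print.** SAP section 10 states "Percentages will be reported to the nearest whole number". Take an arm of 60 subjects aged 65 and over in which 10 have an event after dose 2:
- under the plan: 10/60 = 16.7%, printed 17%;
- among dose-2 recipients if 7 missed dose 2: 10/53 = 18.9%, printed 19%;
- among dose-2 recipients if 2 missed dose 2: 10/58 = 17.2%, printed 17%.

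The printed value first differs at 2 subjects with the event if 7 of 60 missed dose 2 (2/60 prints 3%, 2/53 prints 4%). It first differs at 5 if 2 of 60 missed it (5/60 prints 8%, 5/58 prints 9%), and at 10 if 5 of 100 missed it (10/100 prints 10%, 10/95 prints 11%).

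**The case against.** The strongest reply is that the planned percentage is a legitimate quantity: the share of all vaccinated subjects who had an event in the window. It keeps one N across the table and compares arms without conditioning on something that happens after randomization. Dose-2 recipients are a selected group. Under Protocol 5.2.3, a Grade 3 AE without alternative etiology in the 8 days after dose 1 is among the reasons dose 2 is not given. This point stands as a cost of the change and needs a footnote. It does not justify the present layout, which puts the two quantities side by side unlabelled. The SAP already accepts the same conditioning for solicited events.

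Other points have some force:
- **Table 99 has no footnote of its own.** The opening of SAP section 9 says the denominator will be described for each table, so for Table 99 the denominator is read from the 9.3.2 rule and the title. Nothing points to another denominator.
- **Table 92 is a weak comparator.** Its footnote says "Denominators for percentages are the number of subjects in the safety population who received both the first and second study vaccination", but its McNemar test needs paired data. It shows that missed second doses are expected, and no more. SAP 9.3.1 and Table 77 are the relevant contrast.
- **The 5% and 12% are expectations from earlier trials.** They do not bound this one. A halt to vaccinations under Protocol 9.5 could leave more subjects without dose 2.
- **The practical effect is small.** No test or confidence interval is planned for these tables, many rows will be rare preferred terms, and a reader could recompute from n and the dose-2 counts in Tables 17 and 18.

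**Conclusion.** The concern holds and is minor. The direction is certain: if any subject in an arm misses dose 2 and the event occurs at all, the Post Vac 2 percentage is below the incidence among dose-2 recipients. The relative shortfall equals w. If w is no larger than the planning figures, that is at most 5% for ages 19-64, 7.6% for all ages and 12% for 65 and over, or 1.0, 1.5 and 2.4 percentage points on a 20% incidence. The true w is unknown and probably smaller. The conclusion is firmest for Table 98, where the footnote states the denominator. For Table 99 it rests on the general rule in SAP 9.3.2. It is worth correcting because Table 99 reports a secondary safety endpoint and the SAP already applies the better rule to solicited events.

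**What to change.** In SAP 9.3.2, add a sentence making the denominator for every Post Vac 2 column of Tables 98 and 99 the number of Safety-population subjects who received vaccination 2. Print that N in both shells, as Table 77 does. Keep the full Safety population for the Post Vac 1 and any-vaccination columns. Add a footnote to both tables saying that Post Vac 2 percentages are conditional on receiving dose 2, and that this group is partly selected for having tolerated dose 1.

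The cost is one sentence and two shell footnotes, using counts already produced for Tables 17 and 18. The downside is that the Post Vac 1 and Post Vac 2 columns will describe slightly different groups, which the footnote discloses.
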